8.2. Secondary objective(s)

Safety

- To evaluate the time to cardiovascular events of interest in OSA patients exposed to OZAWADE® as per SmPC compared with OZAWADE® unexposed OSA patients.
- To evaluate the time to adverse drug reaction (serious and non-serious) in OSA patients exposed to OZAWADE® as per SmPC compared with OZAWADE® unexposed OSA patients.

8.3. Exploratory objective(s)

Effectiveness

- To evaluate the effectiveness of OZAWADE® through the Epworth Sleepiness Scale (ESS) when used as per SmPC in patients with OSA.
- To evaluate the effectiveness of OZAWADE® through the Maintenance of wakefulness test (MWT) when used as per SmPC in patients with OSA.
- To evaluate the effectiveness of OZAWADE® through the Multiple Sleep Latency Test (MSLT) when used as per SmPC in patients with OSA.
- To evaluate the effectiveness of OZAWADE® through the Fatigue Severity Scale (FSS) when used as per SmPC in patients with OSA.

Adherence

- To evaluate the adherence to OZAWADE® when used as per SmPC in patients with OSA.
- To evaluate the adherence to continuous positive airway pressure (CPAP) / mandibular advancement devices (MAD), between the group of patients exposed to OZAWADE® and the group of patients not exposed to OZAWADE®.

Other

• To evaluate the reduction of car/traffic accidents.

9. Research methods

9.1. Study design

9.1.1. Overall Design of the Study

This is a prospective, observational, multi-center, open-label, long term, cohort study (OZAWADE® exposed and OZAWADE® unexposed) designed to collect data on the long-term safety of OZAWADE® treatment. This study will be conducted in OSA patients with EDS whose EDS has not been satisfactorily treated by, or who have not tolerated OSA primary therapy. The study will be conducted by physicians specialized in sleep management such as sleep specialists, pulmonologists, cardiologists, otorhinolaryngologist and neurologists.

[figure not shown]
As an observational study, the assignment of the patient to a particular therapeutic strategy should be decided within the current clinical practice and the decision to prescribe OZAWADE® should necessarily precede and be independent of the decision to enrol the patient into the study. OZAWADE® should be prescribed and used based on the routine clinical practice as well as on the individual situation of each patient, according to the approved SmPC.

During the 2-year enrolment phase, 502 patients are planned to be recruited in four to five countries where OZAWADE® is on the market (*i.e.*, France, Germany, Italy and possibly Netherlands, Belgium or Spain), in approximately 8 to 15 centers per country.

Once eligible patients are enrolled, baseline data should be collected. Data collected in the CRF will correspond to data collected in routine practice in the investigating centers.

Patients will be followed-up up to five years, during which time they should be assessed by their treating participating physicians at 6, 12, 24, 36, 48 and 60 months, to follow routine care schedule.

Study visits, procedure and evaluations are summarized in the study flow (Figure 1) and schedule of assessments below (Table 2).

CPAP: Continuous Positive Airway Pressure; EDS: Excessive Daytime Sleepiness; FU: Follow-up; MAD: Mandibular Advancement Device; OSA: Obstructive Sleep Apnoea.

Figure 1: Study Flow.

PASS Protocol [P21-02/OZAWADE]

OZAWADE

Table 2. Schedule of Assessments

	Procedures ¹ /Visits	Inclusion	FU 6 Months	FU Year 1	FU Year 2	FU Year 3	FU Year 4	FU Year 5	End of study
	Visit window		6M [3-9M[12M [9-18M[24M [18-30M[36M [30-42M[48M [42-54M[60M [54-66M[
	Demography: age, gender	X	ē.						
	Profession / Socio-economic status	Х							
Patient interview	Height², weight	Х	Х	Х	X	X	X	X	Х
nten	Waist circumference	X	х	Х	X	X	X	х	Х
anti	Smoking status ³	X ₃	X ³	X ³	X ₃	X ₃	X ₃	X ₃	X ³
Patie	Alcohol consumption	X	х	Х	X	X	X	X	х
	Physical activity	Х	Х	X	X	X	X	X	Х
	Relevant medical history	X							
	Prior medications (last three months)	X							
	Relevant concomitant medications	X	Х	Х	X	X	X	X	Х
e e	Physical examination	X		Х	X	X	Х	X	х
minati	All Adverse Events including adverse events of special interest ⁴		х	х	х	х	X	x	х
l exa	Blood pressure, heart rate	X	Х	Х	X	X	X	X	X
Medical examination	Biological assessment of less than 12 months (cholesterol, glycemia and triglycedemia)	х		х	х	х	х	х	Х
	ECG brought by the patient when available (QT measure) ⁵	X _e	X ⁶	X ⁶	X _e	Xe	Xe	X _e	X _e

PASS protocol Version 3.0 – 23 NOV 2023

PASS Protocol [P21-02/OZAWADE]

OZAWADE

	Procedures /Visits Visit window		FU 6 Months	FU Year 1	FU Year 2	FU Year 3	FU Year 4	FU Year 5	End of study
			6M [3-9M[12M [9-18M[24M [18-30M[36M [30-42m[48M [42-54[60M [54-66[
OSA and sleep history	OSA and sleep history, duration of sleep	X	X ⁷	Х	х	X	Х	Х	Х
	Apnoea-hypopnea index (AHI) At diagnosis of OSA At follow-up visits (with or without CPAP) ⁸	х	х	х	х	х	x	х	х
	Epworth Sleepiness Scale (ESS)	X	X	Х	Х	Х	Х	Х	Х
	CPAP or alternative (e.g., MAD) and adherence ⁹	Х	х	х	х	х	х	х	X
	Maintenance of wakefulness test (MWT) or Multiple Sleep Latency Test (MSLT)	X		х	х	X	х	х	X
	Beck Depression Inventory	Х		Х	Х	Х	Х	Х	Х
	Fatigue Severity scale	X		Х	Х	Х	Х	X	Х
	Assessment of perceived sleepiness at driving	X		х	х	х	х	х	X
OZAWADE* use	Prescription (when applicable)	X							
	Adherence with the Morisky Medication Adherence Scale 8-item (MMAS-8)		х	х	х	х	х	x	х

- 1. Data collected in the CRF will correspond to data collected in routine practice in the investigating centers.
- Height at inclusion visit only.
- 3. Smoking status: in pack-year.
- 4. Adverse events of special interest include the following cardiovascular events: acute myocardial infarction, new onset of angina, unstable angina, stroke (ischemic, haemorrhagic), transient ischemic attack, new onset atrial fibrillation, unscheduled interventional cardiology procedure (stenting, CABG), new onset hypertension (with new hypertension treatment or a posology adjustment of hypertension treatment), new onset or worsening of peripheral vascular disease or unscheduled intervention, stent thrombosis, heart failure, QT prolongation and cardiovascular death.
- 5. ECG when available.
- 6. Last test available at the time of the visit.
- 7. Duration of sleep.
- 8. Although the data will be limited for patients not using primary therapy, the data can be systematically collected from CPAP softwares in those under CPAP during the follow-up visits.
- 9. CPAP or alternative primary treatment adherence will be reported as the mean number of hours of use per night.

PASS protocol 3.0 – 23 NOV 2023

9.1.2. Primary, secondary and exploratory endpoints

9.1.2.1. Primary endpoint

The primary endpoint will be the occurrence of at least one cardiovascular event (CVE) or one serious drug related adverse event during the five years of follow up for each participating patient.

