8.1. Primary objective

The primary objective of this study is to demonstrate that OZAWADE® supplementation in obstructive sleep apnoea (OSA) patients does not increase the incidence of cardiovascular events (CVE) compared with OZAWADE® unexposed patients (non-inferiority) and to evaluate the long-term safety of OZAWADE® when used as per SmPC in patients with OSA.

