9.4. Data sources

This is a prospective, observational study, and patient data collected from the participating physicians will be abstracted from medical records and from administration of baseline and follow-up assessments and questionnaires (PROs and ClinROs).

The patient data will be collected from the patient medical file (original files, hospital reports, laboratory tests reports, various correspondence, etc.). Data will be entered into the electronic case report form (eCRF) using electronic data capture (EDC) via an internet browser interface.

Patients participating in the study will be identified by a unique number (pseudonymized).

[figure not shown]
Sites will be trained to the use of the eCRF. Data will be recorded by participating physicians or qualified designee.

All original source documents from which the information reported in the eCRF will be obtained must be kept up-to-date and readily available. By signing the eCRF, the participating physician will confirm the accuracy, completeness, legibility, and timeliness of the data reported to the Sponsor.

Paper PRO and ClinROs questionnaires will be used and answers will be recorded directly into the eCRF by the sites.

A yearly blinded review of the adverse events and adjudication of the events (major adverse cardiovascular events [MACE] and non-major adverse cardiovascular events [non-MACE]) will be centrally performed by an Independent Committee.

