9.7.5. Primary Analyses

The main objective of the study is to demonstrate that OZAWADE® supplementation does not increase CV events compared with control (non-inferiority). The following analysis will be conducted:

The annual CV morbidity incidence will be estimated by the occurrence of CVE per patient per year equivalent to the proportion of patients with at least one CVE.

The CV risk is known to be higher for OSA patient with existing CV history, using or not CPAP, and well-known risk factors: diabetes, cholesterol, weight, hypertension, demographics (age, gender), lifestyle (fitness, alcohol use, smoking habits).

A generalized linear mixed model featuring Poisson regression will be based on a post stratification model based on the following fixed covariates or random effects:

- nCVE_b, prior CV history measured by the number of CV events experienced before baseline, expected as the essential predicting covariates;
- Risk factors (RF): diabetes, cholesterol, weight, hypertension, alcohol use, and smoking habits reported at baseline;
- Demographics: gender, age, country, study center
- Matched classes propensity clusters: the treatment will be non-randomized but determined by the investigator, involving an expected imbalance between groups on baseline conditions. The decision of prescribing a given medicine will be assumed on a set of baseline covariates defined in the statistical plan. As too many covariates are expected, finding sufficient exact matches is unfeasible, and the goal of subclassification is to form matched subclasses (clusters), such that in each the distribution of covariates for the treated and control groups are as similar as possible. The propensity score will be used as the scalar distance with a two-stage algorithm starting with the nearest neighbour matching and optimized by a full matching procedure [39, 40, 41].

The final model is:

CVE ~ $nCVE_b + \Sigma_i RF_i + gender + age + trt + \{country\} + Offset (log-exp) + \{center | country\} + \{cluster\}$

The notation Σ_i RF_i covers the above mentioned considered risk factors. The obvious effect of the exposure duration is measured by the offset of its logarithm. The last fixed factor is the treatment (trt) binary effect (0=control, 1=pitolisant). Country, site effect nested within country, and cluster (matched group) effects will be used as random factors (between {}).

Sensitivity Analysis

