11.2.2. Causality Assessment

The participating physician is obligated to assess the relationship between study treatment and each occurrence of each AE/SAE. The causality assessment is one of the criteria used when determining regulatory reporting requirements.

The following definitions will be used to assess the relationship of the above mentioned AE to the use of OZAWADE®:

 Related: an AE where there is evidence to suggest a causal relationship between the product and the AE; • **Not related:** an AE where there is no evidence to suggest a causal relationship between the product and the AE.

In case of suspected causal relationship to OZAWADE®, follow-up by the participating physician is required until the event or its sequelae resolve or stabilise at a level acceptable to the participating physician.

If the participating physician's final determination of causality is unknown and the participating physician does not know whether or not OZAWADE® may have contributed to the event, then the event will be handled as "related to OZAWADE®" for reporting purposes.

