11.4.2. Reporting of events to Sponsor Pharmacovigilance

11.4.2.1. Initial reporting

Participating physicians must report to Bioprojet Pharma pharmacovigilance all the following events using the dedicated reporting form:

- All SAEs related and non-related to OZAWADE®;
- All related non-serious AEs (Adverse Drug Reactions);
- All AESIs (as defined in **Section 11.1.4**) related or not, serious or not;
- All SSs including pregnancy cases (as defined in Section 11.1.3).

Safety Event	Collected on the eCRF	Reported on the dedicated Form to Bioprojet Pharma Pharmacovigilance
Non-Serious AEs	All AEs related or not	Only the related AEs - within 7 calendar days of awareness
SAEs	All SAEs related or not	All - within 24 hours of awareness
AESIs	All AESIs related or not, serious or not	All - within 24 hours of awareness
SSs (including pregnancy cases)	All SSs related or not (regardless of whether associated with an AE)	All - within 24 hours of awareness

All SAEs, AESIs, and SSs (including pregnancy cases) will be recorded and reported to Bioprojet Pharma or Designee immediately and under no circumstance no later than 24 hours of awareness.

The primary mechanism for reporting SAEs, AESIs, and SSs (including pregnancy cases) to Bioprojet Pharma pharmacovigilance will be the electronic data collection tool. If the electronic system is unavailable, then the site will use the paper AE or the paper SAE (according to the event reported) data collection tool in order to report the event within 24 hours and will send it to [contact].

All non-serious related AEs will be recorded and reported to Bioprojet Pharma or Designee immediately and under no circumstance no later than 7 calendar days of awareness.

All AEs will be processed by Bioprojet Pharma according to their relevant Standard Operating Procedures. This includes the follow up of AE reports with the participating physicians, as required.

If an AE occurs with a "non Bioprojet Pharma product", the participating physician should consider informing the competent authority in the Member State where the event occurred or the marketing authorisation holder of the suspected medicinal product, but not to both (to avoid duplicate reporting).

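### The protocol fixes two different primary outcomes, and one of them includes a component that patients who never take OZAWADE cannot have

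*Protocol*

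**What the plan says.** **Endpoint.** Protocol Section 9.1.2.1, repeated in the abstract (Section 4), defines the primary endpoint as "the occurrence of at least one cardiovascular event (CVE) or one serious drug related adverse event during the five years of follow up". Under its statistical method, the abstract says that the main endpoint is compared between OZAWADE users and non-users by Poisson regression. Section 9.1.2.2 introduces the secondary endpoints as the separate parts of what the primary endpoint captures together, so the composite looks deliberate.

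**Objective and analysis.** The comparative clause of Section 8.1 is that OZAWADE "does not increase the incidence of cardiovascular events (CVE) compared with OZAWADE® unexposed patients (non-inferiority"). A second clause adds evaluation of long-term safety, with no comparator. Section 9.7.5 restates the aim: "The main objective of the study is to demonstrate that OZAWADE® supplementation does not increase CV events compared with control (non-inferiority"). It then estimates the proportion of patients with at least one CVE and writes a model with CVE as the response.

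**Relatedness.** Section 11.2.2 says "The participating physician is obligated to assess the relationship between study treatment and each occurrence of each AE/SAE", and for the scale itself "The following definitions will be used to assess the relationship of the above mentioned AE to the use of OZAWADE". Section 11.4.2.1 equates relatedness with drug reactions: "All related non-serious AEs (Adverse Drug Reactions"). Section 9.4 provides for "A yearly blinded review of the adverse events and adjudication of the events" as MACE or non-MACE by an independent committee. It does not mention adjudication of relatedness.

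**Secondary comparison.** Section 8.2 sets the aim "To evaluate the time to adverse drug reaction (serious and non-serious) in OSA patients exposed to OZAWADE® as per SmPC compared with OZAWADE® unexposed" patients. Section 9.1.2.2 lists time to adverse drug reaction (ADR) and time to serious adverse drug reaction (SADR).

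**The concern.** A between-group comparison is interpretable only if both groups can have the event. Here half of the composite is defined by attribution to the drug that only one group takes. Patients who never take OZAWADE contribute CVEs alone, while exposed patients contribute CVEs plus serious reactions of any kind. The attribution is made by the treating physician, who knows the exposure because the study is open-label.

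The protocol also does not settle whether this composite or CVE alone carries the non-inferiority conclusion. Two analysts could follow different sections and report different primary results from the same data. If the composite were used, non-cardiovascular reactions could decide a question posed about cardiovascular risk.

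**Working it through.** **Step 1: set the sections side by side.**

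| Place | Outcome compared |
|---|---|
| Section 9.1.2.1 and abstract, primary endpoint | CVE or serious drug-related event |
| Abstract, statistical method | The main endpoint, users against non-users |
| Section 8.1, non-inferiority clause | CVE |
| Section 9.7.5, aim, estimate and model | CVE |

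The serious drug-related component never enters the model in Section 9.7.5. The two definitions cannot both be primary.

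**Step 2: who can have the second component.** The only causality scale (Section 11.2.2) refers to OZAWADE. Section 11.4.2.1 sends events with other companies' products to the authority or to the holder of that product's authorisation. No scale covers other drugs or the unexposed state. A never-exposed patient therefore cannot qualify. A patient unexposed at inclusion who starts later can, because Section 9.3.7.1 collects later starts.

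**Step 3: size of the tilt if the composite is compared.** There is no protocol figure to reproduce: the public text of Section 9.5 and Appendix 1 shows no event rate, margin, alpha or power. The following are assumptions:

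- p is the five-year CVE risk, equal in both groups (no cardiovascular effect).
- q is the risk of a non-cardiovascular serious reaction in exposed patients, independent of CVE.
- The comparison group is never exposed.

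Exposed risk = 1 − (1 − p)(1 − q) = p + q(1 − p). Unexposed risk = p. Risk ratio = 1 + q(1 − p)/p.

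- p = 0.30, q = 0.02: 0.314/0.30 = 1.05
- p = 0.20, q = 0.03: 0.224/0.20 = 1.12
- p = 0.20, q = 0.05: 0.240/0.20 = 1.20
- p = 0.10, q = 0.05: 0.145/0.10 = 1.45

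The planned model works with rates. As a rate ratio, ln(1 − exposed risk)/ln(1 − p), the first and last cases are 1.06 and 1.49. With CVE alone the expected ratio is 1.00 whatever q is.

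**Step 4: illustrative effect on power.** Section 9.9 gives 195 patients per group. Assume a non-inferiority test on the risk difference at one-sided alpha 0.025, with the margin set for 80% power when q = 0: margin = (1.96 + 0.84) × √(2p(1 − p)/195). For p = 0.20 this is about 0.1135. Power = Φ[(margin − q(1 − p))/SE − 1.96], where SE is the unpooled standard error. For p = 0.20, q = 0.02: SE = √((0.16 + 0.1693)/195) = 0.0411, and (0.1135 − 0.016)/0.0411 − 1.96 = 0.41, giving 66%.

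| p | Risk ratio at q = 1%, 2%, 5% | Power at q = 1%, 2%, 5% |
|---|---|---|
| 10% | 1.09, 1.18, 1.45 | 69%, 57%, 23% |
| 20% | 1.04, 1.08, 1.20 | 73%, 66%, 42% |
| 30% | 1.02, 1.05, 1.12 | 75%, 70%, 52% |
| 40% | 1.02, 1.03, 1.08 | 76%, 72%, 59% |

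**Step 5: time to ADR and SADR.** Against never-exposed patients the comparator has no possible events, so a hazard ratio has no meaning there. Any ADR or SADR in an initially unexposed patient must follow a late start, and so is an event on OZAWADE.

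**The case against.** **The model already uses CVE only, so the tilt may be zero.** This is right if Section 9.7.5 governs, and it is why a reader should not infer that the primary result is biased by construction. The bias is conditional on the composite being analysed. The abstract points that way and Section 9.7.5 does not. The contradiction itself stands either way.

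**The objective is not purely cardiovascular.** Section 8.1 does include long-term safety, and the composite may be an attempt to serve both aims. But only the cardiovascular clause carries a comparison. The safety clause supports reporting reactions in exposed patients and does not require adding them to a comparative composite.

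**The control count need not be zero.** Late starters may have OZAWADE-related events, and the protocol does not say how the binary treatment term classifies them; that may be left to the analysis plan. The structural zero applies to never-exposed patients. Section 9.7.6 also describes its Cox model in general terms and does not spell out an ADR hazard ratio. The fault lies in the comparison that Section 8.2 asks for.

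**Serious reactions are real harm.** If q is a true rate, the drug is not harmless, and counting such events in a safety study is legitimate. The accurate statement concerns a drug with no cardiovascular effect. Counting the harm is sound, but comparing it with people who cannot have it is not.

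**The magnitudes are invented.** Both p and q are assumptions. The CVE list is broad (new hypertension, QTcF above 450 ms), which favours a higher p and a smaller tilt; 1.45 pairs the lowest p with the highest q shown. The figures show direction and sensitivity and do not forecast the result.

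**Conclusion.** The point holds as an internal contradiction with a conditional bias. Sections 9.1.2.1 and 4 fix a composite, while the non-inferiority clause of 8.1 and the model in 9.7.5 use CVE. The added component is out of reach for never-exposed patients and rests on attribution by an unblinded physician. Section 11.2.2 handles unknown causality as related for reporting purposes; if that rule were carried into the analysis, the asymmetry would grow.

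If the composite is compared, the expected risk ratio with no cardiovascular effect runs from 1.05 (p = 0.30, q = 0.02) to 1.45 (p = 0.10, q = 0.05) in the main illustrations, and is as low as 1.02 in the wider grid. These values assume equal CVE risk, independence and no late starters. The power losses also assume a margin and alpha that are not visible.

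A reader might infer that the study could give false reassurance. The documents do not support that: the tilt runs against OZAWADE and makes non-inferiority harder to show. The cost is a primary result that does not answer the cardiovascular question, and an ADR/SADR comparison without a meaningful hazard ratio against never-exposed patients.

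**What to change.** 1. In Section 9.1.2.1 and the abstract, define the primary endpoint as at least one adjudicated CVE during follow-up, matching the non-inferiority clause of Section 8.1 and the model in Section 9.7.5.
2. Serve the long-term safety clause by reporting ADR and SADR incidence per patient-year on OZAWADE, in exposed patients only, including time after a late start. Reword Sections 8.2 and 9.1.2.2, and the matching abstract text, to drop the comparison with unexposed patients.
3. Base any between-group comparison of non-cardiovascular safety on all serious adverse events regardless of causality. Section 9.7.7 already describes these by group.

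**Cost.** The changes are to wording. No new data are needed, because Section 11.4.1 already collects all adverse events, related or not. There would be somewhat fewer primary events in the exposed group. The sample size basis is not visible and should be checked to confirm that its event rate refers to CVE; if it was built on the composite, the calculation must be revisited.
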